Specific aims:

Primary aims:

- Stage 1: To understand postoperative urologic, sexual, and pelvic floor experiences of transgender women
- Stage 2: To validate a questionnaire measuring the frequency and severity of postoperative urogynecologic symptoms in transgender women

Secondary aims:

- To understand the types of urologic, sexual and pelvic floor complaints and their degree of bother
- To evaluate the relationship between procedure technique and symptomatology
- To understand the temporal impact on symptomatology after surgery
- To assess the impact of hormonal therapy or other gender confirming treatments on urologic and pelvic floor symptoms.

Background/significance:

It has been estimated that approximately 1 in 60000 individuals globally suffer from gender dysphoria with male-to-female (MTF) gender dysphoria being 4 times more common than female-to-male (FTM) (1). Oftentimes, these individuals are subjected to social stigmatization, abuse, and a general lack of support, leading to depression and higher than average rates of suicide (2). Partially for these reasons, currently only about 13% of transgender patients undergo genital surgery for cosmetic purposes with or without gonadectomy, known as gender confirmation or reassignment surgery (GCS) (3). While some patients elect to forgo gender confirmation surgery voluntarily, others who do desire it are hindered due to cost, availability of trained providers, or the challenges in meeting the WPATH (World Professional Association for Transgender Health) guidelines for transitioning. Patient satisfaction following surgery is high, particularly regarding sexual and cosmetic outcomes; however, unexpected negative functional outcomes such as bowel and bladder dysfunction and sexual impairment can impact overall patient satisfaction (4,5).

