Male-to-female genital surgery typically includes bilateral orchiectomy, penectomy, urethroplasty, labioplasty, and creation of a neovagina and neoclitoris. This can be done in one or two stages with the potential for additional reconstructive procedures in the future. Of the various vaginoplasty techniques available, the type most commonly performed involves vaginoplasty using penile skin inversion and clitoroplasty utilizing the glans penis and preserved neurovascular bundle. Other vaginoplasty techniques involve use of bowel, skin, or cheek mucosal graft. The penile portion of the urethra is amputated, followed by excision of posterior corpus spongiosum and marsupialization of the distal urothelium to the anterior skin flap (1). Bleeding and stenosis of the urethral meatus are complications associated with this approach to urethroplasty (6–9). Subsequent follow-up of patients has shown an increased risk for voiding dysfunction, abnormal urinary stream, incontinence,

and overactive bladder during both the immediate and long-term postoperative period (6,7,9–11). Thus far, postoperative urologic evaluations of MTF patients are based on retrospective analysis, single-provider samples, and simple urologic questionnaires that have no validation within this population. A recent systematic review noted that the majority of literature on outcomes was low to intermediate quality with poor comparability due to differences in data collection and surgical technique (12). The available information suggests that 16-33% of patients experience incontinence postoperatively, with stress predominance, 32-47% experience abnormal voiding, and 24-66% experience overactive bladder symptoms (10,13,14).

Outside of the typically assessed voiding symptoms, unique complaints of MTF postoperative patients include obstructive voiding symptoms due to urethral stenosis, persistent perimeatal erectile tissue, and prostatic hypertrophy (6,8,11). Unfortunately, these conditions cannot accurately be evaluated using standard urogynecologic tools, and they have not been thoroughly characterized in prior studies regarding their severity, effect on voiding, and optimal treatment strategies.

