During the focus group sessions, patients will be consented and reminded of confidentiality rules. In the advent that any disclosed information requires

immediate medical or supportive care, the participant will be placed in direct contact with their primary provider for further assistance. This will be explicitly written in the consent form and verbally announced prior to the start of the focus group. Focus group participants will be provided with a light meal and round trip Metrocard® for travel reimbursement.

There will be a separate informed written consent for Stage 2 participants. These will need to be reviewed and authorized by each participating institution prior to distribution.

Participants:

Male-to-female transgender patients who have either undergone or plan to undergo gender confirmative genital surgery.

Stage 1: In-person focus groups comprised of MTF postoperative patients who participate in support groups in various New York City LGBTQ centers. Participants will be selected using homogeneous sampling methods. We will also reach out to online support communities to set up virtual focus groups or phone interviews if feasible. We plan to embed snowballing sampling to permit recommended individuals to participate.

Stage 2: Patients scheduled to undergo gender confirmative genital surgery or recently completed surgery within academic transgender medicine centers in the United States. They will be recruited on a rolling basis.

Sample size/power:

- Stage 1: Three to four in-person/online focus groups, comprising 10-12 participants with possible one-on-one phone interviews until data saturation reached
- Stage 2: Estimated 100-150 patients (approx 10 patients per question)

Inclusion criteria:

- Stage 1 -- Male-to-female transgender women who are at least 4 weeks postoperative following genital surgery for gender confirmation
- Stage 2 -- Male-to-female transgender women who are scheduled to undergo surgery or are within 4 weeks postoperative
- Both stages -- Minimum age 18 years old
- Both stages -- English fluency
- Both stages -- Reliable contact information and/or permanent residence

Exclusion criteria:

- Preexisting pelvic pathology, including abnormal anatomy or baseline voiding dysfunction
- Urinary or intestinal problems prior to surgery lasting greater than 6 weeks

Primary outcomes:

- Stage 1: Characterization of genital, urologic, bowel, and sexual symptoms following male-to-female gender confirmation surgery

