- Stage 2: Validity and reliability testing of new questionnaire

Secondary outcomes:

- Frequency and severity of symptoms
- Relationship between surgical technique and symptoms
- Effect of hormonal therapy usage and symptoms
- Length of time since surgery and development of symptoms

Confounding factors:

Patient age, race/ethnicity, weight, procedure technique, presence of non-iatrogenic causes of symptoms, co-morbidity, mobility restrictions, medication interactions, diet, infection, type and duration of hormonal therapy, prostate size, sexual activity

Research setting:

Focus groups will take place at the Lesbian, Gay, Bisexual and Transgender Community Center on [name].

Stage 2 will be conducted at various academic centers within the United States.

Committed programs include Boston Medical Center and Weill Cornell Medicine.

Study team members will reach out to additional programs at national conferences and through established networks.

All data will be collected and analyzed within Weill Cornell Medicine

Study instruments:

ATLAS.ti qualitative data analysis software (Berlin, Germany)

PFDI-20 (Pelvic Floor Distress Inventory-20)

PFIQ-7 (Pelvic Floor Impact Questionnaire-7)

WHOQOL-BREF (permission for use granted)

Data collection parameters:

DEMOGRAPHICS/ PRE-TREATMENT DETAILS

- Age
- Race/ethnicity
- Height
- Weight
- BMI (body mass index)
- Smoking status
- Sexual activity
- Medications
- Date of surgery
- Type and extent of hormonal therapy usage
- Additional genital surgical procedures

- History of preoperative urologic complaints
- History of prostatic hypertrophy or prostate cancer

POST-TREATMENT DETAILS

- Operative technique
- Complications
- Postoperative care
- Resumption of hormonal therapy
- Urinary tract infections
- Sexual activity
- Medications

Qualitative data analysis:

- Stage 1: transcript coding with thematic analysis
- Stage 2: Continuous variables will be calculated using student's t- test
 - Categorical data and outcomes will be calculated using chi-square analysis
 - Multiple regression analysis will be performed to assess for a correlation between symptomatology and operative technique, hormonal therapy, or demographics
 - The new questionnaire reliability will be challenged with internal consistency testing and 2-week test-retest
 - Construct validity will be challenged with face validity and convergent validity using the other questionnaires

Ethical issues:

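### Graded symptom frequency and severity items have no ordered method in the plan; an unordered chi-square would cost them about 18 to 24 points of power

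*Combined protocol and SAP*

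**What the plan says.** The Stage 2 methods are listed under Qualitative data analysis. One line reads "Continuous variables will be calculated using student's t- test" and the next "Categorical data and outcomes will be calculated using chi-square analysis". A third plans a multiple regression of symptoms on operative technique, hormonal therapy and demographics, without saying whether it is linear, logistic or ordinal. No rank, trend or ordinal method is named.

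The Stage 2 aim is "To validate a questionnaire measuring the frequency and severity of postoperative urogynecologic symptoms in transgender women". The primary outcome is "Stage 2: Validity and reliability testing of new questionnaire". The first secondary outcome is "Frequency and severity of symptoms"; the other three relate symptoms to surgical technique, hormonal therapy and time since surgery. The sample size is given as "Stage 2: Estimated 100-150 patients (approx 10 patients per question" and no power is stated for any symptom comparison. The new questionnaire is to be written from the Stage 1 themes, so its response scale and scoring are not yet fixed, and the plan does not say which of the three methods an individual symptom item would receive.

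**The concern.** Frequency and severity are normally asked in ordered grades (for example never to always, or none to severe). A single graded item is most naturally read as a categorical outcome, and the plan sends those to chi-square. With five grades and two groups, the Pearson test spreads its sensitivity over 4 degrees of freedom and treats a steady shift towards worse grades no differently from an arbitrary reshuffling of them. An ordered test puts 1 degree of freedom on the shift.

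Three of the four secondary outcomes are comparisons of this kind. The sample size comes from a patients-per-question rule, so it contains no allowance for an inefficient test. A real difference between techniques or hormone regimens could be reported as absent mainly because of the test chosen.

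**Working it through.** **Inputs from the plan.** N = 100 to 150. The rule of about 10 patients per question is consistent with 10 × 10 = 100 and 10 × 15 = 150, that is, 10 to 15 items; the item count is not stated. No alpha, power, effect size or standard deviation is given, so there is no power figure to reproduce. The Background gives symptom rates of 16-33% (incontinence), 32-47% (abnormal voiding) and 24-66% (overactive bladder).

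**Assumptions.** Two-sided 5% level, a five-grade item, proportional odds with odds ratio (OR) 2.5, and two equal groups of n women each.

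**Step 1: one item in closed form.** Take the reference grades p as 60/15/10/10/5%. The proportions at or above each successive grade are 40, 25, 15 and 5%. Multiplying each odds by 2.5 gives 62.5, 45.5, 30.6 and 11.6%, so the comparison grades q are 37.5/17.0/14.8/19.0/11.6%.

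- Chi-square noncentrality: n × Σ(p−q)²/(p+q) = n × (0.0519 + 0.0013 + 0.0094 + 0.0279 + 0.0264) = 0.1169n. This is 5.85 at n = 50 and 8.77 at n = 75. On 4 df the power is 46% and 65%.
- Wilcoxon: the probability that a comparison woman has the worse grade, with ties counted half, is 0.6305. The tie-corrected null standard error is 0.0543 at n = 50 and 0.0442 at n = 75, so the standardised shift is 0.1305/0.0543 = 2.41 and 0.1305/0.0442 = 2.95. With standard errors under the alternative of 0.0519 and 0.0423, the power is 68% and 85%.

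Simulation with 4,000 replicates agrees: 45-46% against 68-69% at 50+50, and 65% against 84-85% at 75+75. With no true difference both tests rejected about 5% of the time.

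**Step 2: across the documents' symptom rates.** Here the grades among symptomatic women are split 40/30/20/10, with OR 2.5 and 2,500 replicates per cell.

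| Any symptom, reference group | 50+50: chi-square → Wilcoxon | 75+75: chi-square → Wilcoxon |
|---|---|---|
| 16% | 27% → 48% | 41% → 65% |
| 33% | 44% → 67% | 62% → 83% |
| 47% | 46% → 70% | 68% → 87% |
| 66% | 50% → 73% | 69% → 87% |

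From the unrounded results, the loss runs from 17.5 points (69.2% against 86.7%) to 24.1 points (41.2% against 65.3%). At 16% part of the loss reflects sparse cells: chi-square rejected only 2.3-2.9% of the time when there was no difference.

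**Step 3: check on the mechanism.** A pure trend with 80% power on 1 df has noncentrality (1.960 + 0.842)² = 7.85. The same signal tested on 2, 3 or 4 df has power of about 71%, 64% or 60%.

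**Step 4: do the other named methods share the fault?** On the Step 1 item at 50+50, Student's t-test on integer scores has 67% power against 68% for Wilcoxon. Across the Step 2 table it is at most 5 points below Wilcoxon. The loss belongs to the unordered chi-square.

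**The case against.** The strongest reply is that the plan never sends a graded item to chi-square. The scale does not exist yet, items may be summed into scores, and the unspecified regression could turn out to be ordinal. This stands as far as it goes, and it is why the point is conditional. But the plan names no ordered method at all, and its only stated rule for categorical outcomes is chi-square.

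A second reply is that proportional odds is the most favourable setting for an ordered test. That also stands. If technique changed the grades in a non-monotone way, chi-square could do better. A general shift towards worse grades is nevertheless the natural question for frequency and severity.

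Several stronger readings are tempting, and the documents do not support them:

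- *The main analysis is at risk.* Symptom frequency and severity are secondary. The primary outcome rests on internal consistency, test-retest and comparison with the other questionnaires.
- *The t-test and regression also discard the ordering.* They keep it when applied to scores. A sizeable t-test loss (32-34% against 47-48% at 70+30) appears only for an assumed zero-inflated 0-100 score whose groups differ in prevalence but not in severity. For an assumed sum of 12 correlated items, t-test and Wilcoxon power were 71% and 73% at 50+50.
- *Symptoms are mostly zero.* The Background's "16-33% of patients experience incontinence postoperatively, with stress predominance" points that way, but the same sentence gives 24-66% for overactive bladder, and rates for single symptoms do not make a summed score mostly zero.
- *Intervals will be too narrow because groups are unequal.* One technique predominates, but the plan gives no split and does not say which group is more symptomatic. At an assumed 4:1 split and 16% prevalence, the pooled-variance 95% interval covered 88-90% when the smaller group was the more symptomatic and 98-99% when it was the less symptomatic. Coverage was about 95% with equal groups or no true difference.

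**Conclusion.** The point holds for graded single items. If they are analysed with the unordered chi-square that the plan names for categorical outcomes, about 18 to 24 points of power are lost at an odds ratio of 2.5 with equal groups and N = 100 to 150. The figure rests on assumed grade distributions, an assumed odds ratio, proportional odds and equal groups. At an assumed 4:1 split and the same odds ratio the loss ranged from about 8 to 32 points, largest when the smaller group was the less symptomatic. At an odds ratio of 3.5 with equal groups it was 4 to 24 points, shrinking as power neared its ceiling.

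It does not extend to a general failure of the t-test, regression or intervals, nor to the primary outcome. A reader might also infer that every domain score needs an ordinal model; that is a debatable trade-off which these results do not force.

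**What to change.** Amend the Stage 2 analysis text as follows, once the response scale and scoring are fixed after Stage 1 and before Stage 2 data are analysed:

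- **Graded frequency and severity items, unadjusted:** replace chi-square with the Wilcoxon test (two groups) or Kruskal-Wallis test (more than two), or a trend test where the grouping is itself ordered, as with time since surgery.
- **Graded items, adjusted:** specify the multiple regression as proportional-odds regression and report odds ratios with 95% intervals.
- **Unordered categories:** keep chi-square.
- **Multi-item scores:** mean-based methods may stay. Where a score is zero-heavy and the groups are unequal, add robust or bootstrap intervals or a rank-based check, because pooled-variance intervals can then be too narrow or too wide depending on which group is more variable. Switching to Welch's test is not a clean remedy: on the graded item at 16% prevalence and 4:1 groups it rejected 7-10% of the time under no difference.

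The cost is SAP wording only, with no extra patients or data. The small downside is that graded-item results become odds ratios, and the proportionality assumption has to be checked.

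### The Stage 2 regression on technique and hormones has no centre term, so a centre difference, if there is one, could be reported in part as a technique or hormone association

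*Combined protocol and SAP*

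**What the plan says.** The combined protocol and SAP describes a multicentre Stage 2. The Research setting section puts it this way: "Stage 2 will be conducted at various academic centers within the United States". It then names the two sites that have agreed so far, in these words: "Committed programs include Boston Medical Center and Weill Cornell Medicine". Beyond those two, the list of sites is still to be filled, and the plan for doing so reads: "Study team members will reach out to additional programs at national conferences and through established networks". The final number of centres is therefore open. Research design adds that all sites enter data into one shared database.

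The analysis section, under Stage 2, gives the only description of the model: "Multiple regression analysis will be performed to assess for a correlation between symptomatology and operative technique, hormonal therapy, or demographics". It also plans t-tests and chi-square tests, without saying which comparisons they serve.

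The Confounding factors section lists 13 items, beginning "Patient age, race/ethnicity, weight, procedure technique, presence of non-iatrogenic causes of symptoms, co-morbidity, mobility restrictions". Neither centre nor surgeon is among them, and neither appears in the data collection parameters. No section mentions a centre covariate, stratification by centre, a random effect, clustered standard errors or a by-centre sensitivity analysis.

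The regression serves named objectives. Specific aims includes "To evaluate the relationship between procedure technique and symptomatology" and an aim on hormonal therapy. Secondary outcomes includes "Relationship between surgical technique and symptoms" and, as a separate entry, "Effect of hormonal therapy usage and symptoms".

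**The concern.** Who operates, and so which technique is used, may depend on where the patient is treated. So may hormone practice, case mix, postoperative care and the way symptoms are elicited. A model that omits centre attributes any symptom difference between centres to whichever included variable happens to vary with centre.

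Two conditions must both hold for this to matter. The technique (or hormone) mix must differ between centres, and symptom level must differ between centres by more than the other adjusted factors explain. If either fails, omitting centre does not bias the estimate.

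At stake is the interpretation of the technique and hormone results. The background section itself criticises earlier studies for drawing on one provider and for being hard to compare because techniques and data collection differed. Pooling centres without accounting for them leaves part of that weakness in place.

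**Working it through.** **The plan's own figure.** Stage 2 is sized at 100 to 150 patients, at about 10 per question. That implies 100/10 = 10 to 150/10 = 15 questions. The number of questions is not given, so this can be checked only for consistency. It is not a power calculation for the regression: no effect size, SD, alpha or power is stated.

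**Inputs.** Only N = 100 to 150 comes from the documents. The rest is assumed: two equal centres, a binary technique with shares pA and pB, no true technique or hormone effect, within-centre SD 1, two-sided 5%. The centre gap d, in SD units, is the difference left after the other adjusted factors.

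**Bias from omitting centre.** With mean share p = (pA + pB)/2,

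bias = d × 0.25 × (pB − pA) / [p(1 − p)].

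- Technique 10% vs 30%: 0.25 × 0.20 / (0.20 × 0.80) = 0.05/0.16 = 0.312, so the bias is 0.312 d.
- Technique 10% vs 50%: 0.10/0.21 = 0.476, so the bias is 0.476 d.
- Hormone use 30% vs 70%: 0.10/0.25 = 0.400, so the bias is 0.400 d.
- Equal shares: 0.

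**Worked case, 10% vs 50%, d = 0.5.**

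- Bias = 0.476 × 0.5 = 0.238.
- Residual variance without centre = 1 + 0.5² × (0.25 − 0.10²/0.21) = 1.051.
- N = 100: standard error = √(1.051/(100 × 0.21)) = 0.224, ratio 0.238/0.224 = 1.06, rejection rate about 19%.
- N = 150: standard error = 0.183, ratio 1.30, rejection rate about 26%.

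**Simulation.** Least squares on technique, hormone use, age, BMI and race; 8,000 simulated data sets per scenario. The table gives rejection rates without a centre term, N = 100 then N = 150.

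| Scenario | d = 0.1 | d = 0.2 | d = 0.3 | d = 0.5 |
|---|---|---|---|---|
| Technique 10% vs 30% | 5.4%, 5.1% | 5.9%, 6.4% | 6.1%, 6.8% | 9.0%, 11.0% |
| Technique 10% vs 50% | 5.6%, 5.7% | 7.2%, 8.4% | 10.1%, 12.3% | 18.0%, 25.1% |
| Four centres, technique 10/20/35/50% | 4.9%, 4.9% | 5.5%, 6.0% | 6.7%, 7.3% | 9.7%, 11.3% |
| Hormone use 30% vs 70%, equal technique shares | 5.1%, 5.3% | 6.5%, 7.5% | 8.5%, 11.4% | 16.1%, 21.9% |

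With equal technique shares the rate for technique is 4.6 to 5.5% at every gap. For 10% vs 30% at d = 0.3 and N = 150, the normal approximation gives 7.4% against the simulated 6.8%; hence the summary of about 5 to 8% up to d = 0.3. With a centre term the rate is 4.3 to 5.4% in all scenarios.

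**Cost in precision.** The standard error with a centre term is larger by about 1/√(1 − R²), where R² is the squared correlation of technique with centre.

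- 10% vs 30%: R² = 0.05²/(0.25 × 0.16) = 0.0625, factor 1.03 (simulated 1.01 to 1.04).
- 10% vs 50%: R² = 0.10²/(0.25 × 0.21) = 0.190, factor 1.11 (simulated 1.09 to 1.12).
- 10% vs 80%: R² = 0.175²/(0.25 × 0.2475) = 0.495, factor 1.41 (simulated 1.41 to 1.44).
- Four centres: simulated 1.06 to 1.08.
- Hormone use 30% vs 70%: R² = 0.16, factor 1.09 (simulated 1.07 to 1.10).

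**The case against.** The strongest reply is that the harm is hypothetical and probably small. The background section says penile skin inversion is the usual technique, which makes modest share differences plausible. With an alternative technique at an assumed 5% vs 15% in two equal centres, the false-positive rate is only 5.1 to 6.1% for gaps of 0.1 to 0.3 SD and 6.9 to 7.9% at 0.5 SD. More centres, which the plan seeks, also dilute the effect in the four-centre case above. This stands: the inflation is material only when the share difference and the gap are both large, and nothing in the documents says they are. But the usual technique overall need not have the same share at every centre, and the documents do not settle that.

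Second, a reader might infer that technique and centre effects could not be told apart at all. That goes too far. The listed confounders include age, weight, co-morbidity, infection and prostate size, and postoperative care and complications are recorded. If used, these would absorb part of any centre difference. The plan does not say how they enter the model, so d above has to be read as a residual gap.

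Third, a reader might infer that centre will not be recorded. The documents do not support that. The data collection list is not exhaustive: it also omits co-morbidity, mobility and diet, which the plan names as confounders. Each institution reviews its own consent form and the database is shared, so the source institution may well be known. Likewise, the regression sentence may name only the associations of interest. What stands is that nothing commits the analysis to using centre.

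**Conclusion.** The point holds as a conditional one. The plan pools several centres, technique is not randomised, and the stated model and confounder list leave centre out. If centres differ in both mix and residual symptom level, part of that difference would be reported as a technique or hormone association.

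The likely size ranges from negligible to material. The false-positive rate for technique is about 5 to 8% at 10% vs 30% with gaps up to 0.3 SD, and about 18 to 25% at 10% vs 50% with a gap of 0.5 SD, against about 5% with a centre term. In the scenarios where the omission matters, the rate rises with N, so recruiting to 150 does not help. Every input except N is an assumption.

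Two stronger readings are not supported. The documents do not show that centres differ, so the planned results cannot be called confounded. The primary Stage 2 outcome, validity and reliability of the new questionnaire, does not depend on this regression. This is an inexpensive improvement that should be made, held with medium confidence.

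**What to change.** - Make sure a coded centre field is in the shared database, and add centre to the confounder list.
- Prespecify adjustment for centre in the technique and hormone regressions: a fixed effect if centres are few, a random effect or stratification if there are many small ones. Do not merge dissimilar small centres into one category, because confounding returns inside it. In an assumed case with N = 150 (two centres of 35, four of 20 with shares of 10/20/35/50%, gap up to 0.5 SD), the rate was 7.4% with the four merged and 5.1% with all kept separate.
- Base technique and hormone conclusions on the centre-adjusted model, not on unadjusted t-tests or chi-square tests.
- Report technique and hormone use by centre. Where either coincides with centre, state that its effect cannot be separated from centre.

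The cost is one field, one sentence and one table. The technique standard error grows by about 1 to 12% at moderate share differences (10% vs 30% to 10% vs 50%) and by 41 to 44% at 10% vs 80%. The hormone standard error grows by 7 to 10% at 30% vs 70%. If each centre uses a single technique, a model with fixed centre effects cannot estimate the technique effect, and the report should say so.

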This will be a mixed methods study in an exploratory sequential design structure involving qualitative analysis via focus groups comprised of postoperative transgender women (Stage 1), followed by the distribution and testing of a questionnaire packet to male-to-female patients planning to undergo GCS at academic transgender care centers in the United States (Stage 2). The intent of the Stage 1 focus group questions will be to clarify the presentation and severity of urogynecologic symptoms in this patient group. Moderators will also ask the participants about the type and timing of their gender confirmation surgery, additional procedures, use of hormonal therapies, and neovaginal care. Please review attached Moderator Guide for the concepts to be addressed. The themes and categories generated from the focus groups will be used to create a unique screening questionnaire for this patient population that will be tested for reliability and validity in the Stage 2 component. We estimate that about 3 to 4 focus groups will be required to reach data saturation; however, additional groups may be necessary.

Stage 2 will be conducted in coordination with participating academic medical centers with affiliated gender surgeons or internal transgender care centers with surgical providers. After patient recruitment, postoperative questionnaires will be distributed which will be comprised of the Pelvic Floor Distress Inventory-20 (PFDI-20), Pelvic Floor Impact Questionnaire-7 (PFIQ-7), WHO Quality of Life BREF (WHOQOL-BREF), and the new questionnaire created from the Stage 1. We estimate about 10 minutes will be required to complete the entire questionnaire packet. A test-retest reliability challenge will be performed two weeks later with the new questionnaire only. Patient data and questionnaire answers will be entered into a universal RedCap database. All data will be analyzed at Weill Cornell Medicine. Operative information for Stage 2 participants as well as postoperative exams and treatments will be reviewed at the time of data collection and entered for analysis.

Patient recruitment for Stage 1 will be facilitated by provider referrals through transgender clinics and LGBTQ centers as well as flyer distribution to local support groups and networks (Appendix 1). A website URL (Appendix 2) will be included on the flyer for additional participation information for both Stage 1 and Stage 2.

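### The planned convergence tests give little quantitative validity evidence for the population-specific items; report those items separately and add a supportive known-groups comparison

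*Combined protocol and SAP*

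**What the plan says.** Validity and reliability of the new questionnaire form the Stage 2 primary outcome. Under Qualitative data analysis, Stage 2, the whole construct-validity plan is one line: "Construct validity will be challenged with face validity and convergent validity using the other questionnaires". Research design and Study instruments identify the other questionnaires as PFDI-20, PFIQ-7 and WHOQOL-BREF. Internal consistency and the two-week retest are listed as reliability.

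Background/significance states that "unique complaints of MTF postoperative patients include obstructive voiding symptoms due to urethral stenosis, persistent perimeatal erectile tissue, and prostatic hypertrophy", and then that "these conditions cannot accurately be evaluated using standard urogynecologic tools".

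Research design gives the purpose of the focus-group themes: "create a unique screening questionnaire for this patient population that will be tested for reliability and validity in the Stage 2 component". It also says that "postoperative exams and treatments will be reviewed at the time of data collection and entered for analysis". Data collection parameters add complications and urinary tract infections after treatment.

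The remaining Stage 2 analyses are a t-test line, "Categorical data and outcomes will be calculated using chi-square analysis", and "Multiple regression analysis will be performed to assess for a correlation between symptomatology and operative technique, hormonal therapy, or demographics". None is tied to validity, and the first two name no groups.

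**The concern.** Face validity is a judgement, so convergence carries all the quantitative weight. It is informative where a comparator asks about the same symptom. It is weak where the comparator does not, and the protocol says that standard urogynecologic tools fall short for the very complaints that justify a new questionnaire. WHOQOL-BREF is not a urogynecologic tool, but agreement with general quality of life shows burden rather than that an item measures its intended symptom.

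At stake is what the primary outcome can claim. A good overall correlation could be reported as validation of the whole questionnaire although it came from the ordinary pelvic-floor items. The items that make the instrument new would have content support from Stage 1 and no quantitative check of their own. The clinical information that could supply one is to be entered, but no stated analysis uses it this way.

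**Working it through.** **1. The plan's own figure.** Sample size/power gives 100-150 patients at about 10 per question. 10 × 10 = 100 and 10 × 15 = 150, so the range implies 10 to 15 questions (the count is not stated). The rule sets no target correlation or group difference.

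**2. Which evidence reaches the population-specific items**

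| Planned element | What it offers these items |
|---|---|
| Stage 1 focus groups, to saturation | Content evidence, qualitative |
| Face validity | Judgement |
| Convergence with PFDI-20, PFIQ-7 | Little, on the Background premise |
| Convergence with WHOQOL-BREF | General burden |
| Internal consistency, retest | Reliability only |
| Regression on technique, hormones, demographics | Secondary aims; no predicted direction |

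**3. Can a total score hide these items?** Assumed inputs: the general part correlates 0.7 with the comparator and the specific part 0; s is the weight on the specific part, w = 1 − s, and ρ is the correlation between the parts.

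r(total) = 0.7w / √(w² + s² + 2wsρ)

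- s = 0.20, ρ = 0: 0.56 / √0.68 = 0.68
- s = 0.33, ρ = 0: 0.469 / √0.5578 = 0.63
- s = 0.50, ρ = 0: 0.35 / √0.50 = 0.49
- With ρ = 0.3 the three values are 0.64, 0.56 and 0.43.

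An observed r of 0.70 has a Fisher z 95% interval of 0.58-0.79 with 100 women and 0.61-0.77 with 150. With ρ = 0, totals carrying a fifth or a third of unrelated content (0.68, 0.63) lie inside both. The total would not reveal whether those items are poor or valid for something the comparator misses.

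**4. How precise would a known-groups comparison be?** Assumed inputs: N = 100, a condition in a share p of 10-30%, and a share e = 0.5 examined regardless of condition. The documents give none of these rates. All women: recorded group n1 = Npe, the rest n2 = N − n1. Examined only: n1 against 50 − n1.

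Half-width in SD units = t(0.975, n1 + n2 − 2) × √(1/n1 + 1/n2), with t = 1.984 (98 df) or 2.011 (48 df).

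| p | All women | Half-width | Examined only | Half-width |
|---|---|---|---|---|
| 10% | 5 v 95 | 0.91 | 5 v 45 | 0.95 |
| 20% | 10 v 90 | 0.66 | 10 v 40 | 0.71 |
| 30% | 15 v 85 | 0.56 | 15 v 35 | 0.62 |

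Worked case: 1.984 × √(1/5 + 1/95) = 1.984 × 0.459 = 0.91.

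**5. Unexamined cases in the comparison group.** Their share is p(1 − e)/(1 − pe): 0.05/0.95 = 5.3% at p = 10%, and 0.15/0.85 = 17.6% at p = 30%. Ignoring the small change in SD, a true difference of 0.80 SD becomes 0.80 × 0.947 = 0.76 or 0.80 × 0.824 = 0.66. At p = 10% the expected all-women result is 0.76 ± 0.91, about −0.15 to 1.67. Even a large true difference would not be separated from zero.

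**The case against.** The case against has four parts.

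**Stage 1 already supports these items.** Focus groups run to saturation, with themes turned into items, are content evidence for exactly this material. This stands. A reader might infer that the items would have no validity evidence at all; the documents do not support that. What is thin is the quantitative evidence.

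**The construct is symptoms, not anatomy.** Specific aims set out to measure how often and how severely symptoms occur. Research design's word screening might suggest that an item must detect stenosis or enlarged prostate tissue. One word does not carry that. A recorded finding is a variable related to the symptom, so the comparison can only be supportive. This stands too.

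**Convergence is not empty.** A reader might infer that it can never tell a good item from a poor one, or that it should be abandoned. Neither follows. Comparator coverage can be judged from content once items exist. With coverage held low, assumed values of 0.80 and 0.25 for the item's link to its symptom, and 0.25 for the symptom's link to the comparator, give 0.80 × 0.25 = 0.20 against 0.25 × 0.25 = 0.06. That difference is hard to resolve at this sample size, but it exists. The Background sentence also does not name PFDI-20 or PFIQ-7, and their item content is not in the documents.

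**The added comparison is weak.** Groups may be small, as the working shows. Women enter before surgery or within four weeks after it, and no questionnaire time point is given, so late problems may be few and resolved ones may mix with current ones. Complications is a generic field, prostatic hypertrophy appears only as pre-treatment history, and Ethical issues requires no visits beyond standard care. The exclusion of "Preexisting pelvic pathology, including abnormal anatomy or baseline voiding dysfunction" may thin the groups further. All of this stands. It limits how the result may be read and shapes the fix, but does not remove the reason for reporting it.

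**Conclusion.** The point holds in a limited form. Convergence is the only quantitative construct-validity test planned, and on the protocol's own premise it gives little evidence for items on the population-specific complaints. A total-score correlation could conceal how they perform: 0.68 or 0.63 against 0.70 with a fifth or a third of unrelated weight, under the stated assumptions and ρ = 0. This does not show that the questionnaire would be invalid, or that convergence is uninformative for symptoms the comparators cover.

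A known-groups comparison would add evidence of a different kind, but imprecisely: half-widths of about 0.91-0.56 SD for all women and 0.95-0.62 SD for examined women only. A null result would not show that an item is invalid. These figures rest on assumed condition rates of 10-30%, half of 100 women examined regardless of condition, and Stage 1 producing items on these complaints.

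**What to change.** Add the following to Qualitative data analysis, Stage 2.

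(a) After Stage 1 and before Stage 2 analysis, fix the convergent hypotheses by domain. Treat convergence as a validity test only where a comparator covers the same symptom. Report the population-specific items separately from any total score.

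(b) Compare the relevant item or domain scores between women with and without a related recorded complication, exam finding or treatment, with the direction stated in advance. Count only findings current when the questionnaire was completed, and keep resolved or treated problems as a separate category. Report group sizes, confidence intervals, the number of women with a relevant exam, and both examined-only and all-women results. Label the comparison supportive, with no pass/fail threshold.

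The cost is a few paragraphs and a modest analysis of information the protocol already plans to enter. The database would also need the type and date of each complication or finding, and whether a relevant exam took place. No extra visits are needed. The drawbacks are wide intervals and dependence on standard-care records.
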